10.8 Data and Safety Monitoring and Analysis

10.8.1 Study Monitoring Committee

Data and Safety Monitoring Board oversight is not planned for this study. The MTN SMC will conduct interim reviews of study progress, including rates of participant accrual, retention, completion of primary and main secondary endpoint assessments,

study or lab issues, and a closed safety data report to voting SMC members. The review will take place at least once during the study, and as needed. At the time of this review, or at any other time, the SMC may recommend that the study proceed as designed, proceed with design modifications, or be discontinued. For further information regarding the SMC, please reference the MTN Manual of Operational Procedures (www.mtnstopshiv.org).

10.8.2 Primary Analysis

When the use of descriptive statistics to assess group characteristics or differences is required, the following methods will be used: for categorical variables, the number and percent in each category; for continuous variables, the mean, median, standard deviation, quartiles and range (minimum, maximum). Within-treatment group assessment of the change from the baseline measurement to a follow-up measurement will be analyzed using McNemar's test (for categorical response variables) or the paired t-test or Wilcoxon signed-ranks test (for continuous variables). When use of formal testing to assess differences between users of the placebo VR and users of the dapivirine VR is required, the following methods will be used: for binomial response variables, chi-square tests and logistic regression (or exact testing methods); for continuous variables, t-tests and linear regression or nonparametric methods if data are non-Normal.

To assess the adequacy of the randomization, participants in each of the two arms will be compared for baseline characteristics including demographics and laboratory measurements using descriptive statistics.

Safety Endpoints

All females randomized into the study will be included in the primary analysis according to principle of Intent-to-Treat. To assess safety, the number and the percentages of participants experiencing each safety endpoint will be tabulated by study arm. Each participant will contribute once in each category (i.e., only for the highest severity AE for each participant) for the calculation of event rates. Exact binomial confidence intervals will be calculated for each safety endpoint for each arm and Fisher's exact test used to test for differences in event rates between the two arms.

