10 STATISTICAL CONSIDERATIONS

10.1 Overview and Summary of Design

This is a multi-site, double-blinded, two arm, 3:1 randomized, placebo-controlled trial to assess the safety of dapivirine (25 mg) administered in a silicone elastomer vaginal matrix ring, when inserted once every 4 weeks during 12 weeks of study product use by healthy, sexually active, HIV-uninfected postmenopausal females, as compared with a placebo VR. A total of approximately 96 postmenopausal females (72 in the dapivirine VR arm and 24 in the placebo VR arm) will be randomized.

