10.2 Study Endpoints

Primary endpoints

Consistent with the primary study objective to assess the safety of dapivirine (25 mg) administered in a silicone elastomer vaginal matrix ring, when inserted once every 4 weeks during 12 weeks of study product use by healthy, sexually active, HIV-uninfected postmenopausal females, as compared with a placebo, the primary safety endpoints are the proportion of females in each of the two arms with:

- Evidence of Grade 2 or higher genital, genitourinary and reproductive system AEs as defined by the Division of AIDS Table for Grading the Severity of Adult and Pediatric Adverse Events, Version 1.0, Dec 2004 (Clarification dated August 2009), Addendum 1, (Female Genital Grading Table for Use in Microbicide Studies) judged to be related to study product
- Evidence of Grade 3 or higher AEs as defined by the Division of AIDS Table for Grading the Severity of Adult and Pediatric Adverse Events, Version 1.0, Dec 2004 (Clarification dated August 2009)

Secondary endpoints

Consistent with the secondary study objective to evaluate acceptability of study VR expressed as women's preference for the VR compared to other HIV prevention methods in HIV-uninfected postmenopausal women, the following endpoint will be assessed:

- The proportion of participants who find the study VR to be as acceptable as other HIV prevention methods

Consistent with the secondary study objective to evaluate the adherence to the dapivirine VR versus the placebo VR for 12 weeks of continuous use, the following endpoint will be assessed:

- Adherence measures of daily study product use based on self-report for each participant over the study product use period

Consistent with the secondary study objective to evaluate the systemic and local dapivirine exposure, the following endpoint will be assessed:

- Dapivirine concentrations in plasma, vaginal fluid and cervical tissue

Exploratory Endpoints

Acceptability

- Participant's self-report on multiple components of acceptability via attitudinal questions

Adherence

- Residual amount of dapivirine measured in returned VRs
- Dapivirine concentrations in plasma, vaginal fluid, and cervical tissue

Vaginal Microenvironment

- Changes in pH, microflora and biomarkers

Note: Cervical tissue will be collected on a subset of participants taking part in the Cervical Biopsy/Vaginal Fluid Subsets

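### Change from baseline is tested within each arm, and the named between-arm methods are not tied to the Enrollment value: a low-severity, no-cost improvement for the exploratory microenvironment endpoint

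*Protocol*

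**What the plan says.** Protocol section 10.8.2 is a general list of methods. For change over time it states: "Within-treatment group assessment of the change from the baseline measurement to a follow-up measurement will be analyzed using" McNemar's test for categorical responses, and the paired t-test or Wilcoxon signed-ranks test for continuous ones.

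A separate sentence covers comparison of the arms. It applies conditionally ("When use of formal testing to assess differences between users of the placebo VR and users of the dapivirine VR is required"). It offers chi-square tests and logistic regression, or exact methods, for binary responses, and "for continuous variables, t-tests and linear regression or nonparametric methods if data are non-Normal". It does not mention change, baseline or covariates.

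The endpoint defined as a change is "Changes in pH, microflora and biomarkers" (section 10.2). It is exploratory and serves a descriptive objective in section 3.3. Section 10.8 has no paragraph of its own for it, so the within-arm sentence is the only analysis text that speaks of change from baseline.

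Table 5 and Appendix I show that pH, Gram stain, quantitative culture and biomarkers are all sampled at Enrollment. The first three are repeated at Weeks 4, 8 and 12, and biomarkers at Weeks 4 and 12. Section 10.1 gives the arm sizes: "72 in the dapivirine VR arm and 24 in the placebo VR arm".

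**The concern.** A within-arm test of change cannot separate a drug effect from the effect of wearing any ring, or of time. The placebo ring is there to make that separation. Under 3:1 allocation the within-arm tests also have unequal power. A change common to both rings can then easily appear significant in the larger arm and not in the smaller one. A reader shown the two p-values side by side may take that for a dapivirine effect on the vaginal environment.

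The second issue is precision. Any comparison of the arms is limited by 24 placebo women. Their Enrollment values are already in hand, but section 10.8.2 does not say that the between-arm analysis will use them.

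**Working it through.** **Inputs.** Arm sizes 72 and 24 come from section 10.1. The protocol gives no SD, effect size, baseline correlation or power figure for any change endpoint. The standardised changes (0 to 0.8 SD of the change) and the baseline-to-follow-up correlations ρ (0.3 to 0.7) are therefore assumptions, shown as ranges.

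**Step 0: the plan's own figures.** The nearest stated figure is Table 12 (two-sided Fisher's exact test, α = 0.10, 24 versus 72). At a placebo rate of 4.2%, exact power is 80.3% at a drug-arm rate of 26.3% and 90.2% at 30.2%, so the table reproduces. It concerns the primary safety endpoints and is not in question here.

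**Step 1: power of the two within-arm tests.** Give both arms the same true standardised change d. Power of the paired t-test (two-sided 5%) comes from the noncentral t distribution with n − 1 degrees of freedom and noncentrality d√n. The arms are independent, so

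P(significant on dapivirine only) = power at 72 × (1 − power at 24).

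| d, same in both arms | Power, n = 72 | Power, n = 24 | Dapivirine only |
|---|---|---|---|
| 0 | 5.0% | 5.0% | 4.8% |
| 0.2 | 38.8% | 15.6% | 32.7% |
| 0.3 | 70.9% | 29.1% | 50.3% |
| 0.4 | 91.7% | 46.7% | 48.9% |
| 0.5 | 98.7% | 65.0% | 34.5% |
| 0.6 | 99.9% | 80.4% | 19.6% |
| 0.8 | 100% | 96.3% | 3.7% |

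For example, at d = 0.4: 0.917 × (1 − 0.467) = 0.489. The pattern is common for moderate shared changes and fades when the change is large enough for 24 women to show it.

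**Step 2: is the direct between-arm test sound?** In 20,000 simulated trials per ρ at 72 versus 24 (normal data, equal variances, no arm difference), the two-sample t-test rejected in 0.047 to 0.050 of runs, for follow-up values and for change scores alike. It holds its 5% level. Only precision is at stake there.

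**Step 3: what the Enrollment value would add.** With equal SDs at baseline and follow-up, the large-sample variance of the arm difference is proportional to 1 for follow-up values, 2(1 − ρ) for change scores, and 1 − ρ² for regression on arm and baseline. The detectable difference (80% power, two-sided 5%, normal approximation) is

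(1.960 + 0.842) × √(1/24 + 1/72) × √(variance factor) = 0.66 × √(variance factor), in SD units.

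| ρ | Follow-up t-test | Change-score t-test | Baseline-adjusted regression | Variance cut vs change score | Variance cut vs follow-up |
|---|---|---|---|---|---|
| 0.3 | 0.66 | 0.78 | 0.63 | 35% | 9% |
| 0.5 | 0.66 | 0.66 | 0.57 | 25% | 25% |
| 0.7 | 0.66 | 0.51 | 0.47 | 15% | 49% |

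For example, at ρ = 0.3: 0.91/1.40 = 0.65 against the change score, a 35% cut, and 0.91/1 against the follow-up value, a 9% cut. Both comparators are shown because section 10.8.2 does not say which outcome its t-test would use, and the trend across ρ runs in opposite directions for the two.

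**The case against.** A reader might infer that the plan compares arms by an unadjusted t-test alone and so builds in a false dapivirine signal. The document does not support that.

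- **A direct comparison of the arms is provided.** Section 10.8.2 gives it a sentence of its own, and nowhere does the protocol say that an arm difference will be deduced from two within-arm p-values. The percentages in Step 1 describe a pattern that misleads only someone who reads the tests that way. This stands, and Step 2 confirms that the direct t-test keeps its level.
- **Regression is already named.** Linear and logistic regression, nonparametric and exact methods are listed beside the t-test and chi-square test. Regression can carry a baseline value. Adjustment is neither specified nor excluded. This stands.
- **The endpoint is exploratory and its objective is to describe.** Within-arm change answers a descriptive question. The primary endpoints use Fisher's exact test, and adherence (section 10.8.3) uses a between-arm difference with its 95% interval. Neither is touched. This stands and sets the severity. A descriptive aim does not, however, call for within-arm significance tests.
- **Covariates may properly be left to the analysis plan**, which is not at hand. This stands for the precision point. It has less force for the within-arm tests, because there the protocol has already chosen the method.
- **The magnitudes are assumed.** They are, and they are given as ranges for that reason.

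**Conclusion.** The point holds as a low-severity improvement. The only method that section 10.8.2 ties to change from baseline is a test within each arm. At 72 versus 24 women those tests have such unequal power that a shared change of 0.3 to 0.5 SD gives significance on dapivirine only in about 35 to 50% of trials, against about 5% with no change. They are no evidence of an arm difference. The between-arm methods are valid, but they are not linked to the Enrollment values that the schedule already collects. Using those values would reduce variance by 15 to 35% relative to a change-score t-test, or by 9 to 49% relative to a follow-up-value t-test.

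These sizes rest on assumed effects and correlations, normal data, equal SDs and the full 72 and 24 women. Losing 5% under the retention target would raise every detectable difference by a factor of about 1/√0.95 = 1.03. The power figures are for the paired t-test and the precision figures for continuous measures. McNemar's test, the Wilcoxon test and logistic regression were not computed. The conclusions about primary safety do not change.

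**What to change.** Add a sentence or two to section 10.8.2 with two elements:

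1. Within-arm changes in pH, flora and biomarkers are descriptive summaries, reported without p-values.
2. Any comparison of the arms on these measures uses the linear regression already named (logistic for categorical measures), with the follow-up value as outcome and arm and the Enrollment value as covariates. The estimated arm difference (or odds ratio) is reported with its 95% confidence interval.

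If the analysis plan already says this, section 10.8.2 need only be brought into line with it. The cost is editorial: no new data, visits or participants, and no change to the primary analysis.

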10.4 Sample Size and Power Calculations

10.4.1 Primary Endpoints

The proposed total sample size is approximately N=96 postmenopausal females randomized to 2 arms in a 3:1 ratio giving 72 postmenopausal females in the dapivirine VR arm and 24 postmenopausal females in the placebo VR arm. The sample size is based upon the size of similar Phase 2a studies of vaginal microbicide products and includes a 3:1 ratio of drug to placebo arms to allow for the collection of additional safety endpoints in the drug arm while maintaining blinding between arms.

As a means to characterize the statistical properties of this study Table 10 presents the probability (expressed as a percent) of observing zero, at least one, and two or more safety endpoints among the 72 postmenopausal females in the dapivirine VR arm for various 'true' event rates.

Table 10: Analysis of Safety Event Frequency

Event Rate (%)	P (0 events n=72) (%)	P (≥ 1 event n=72) (%)	P (≥ 2 events n=72) (%)
0.5	69.7	30.3	5.1
1.0	48.5	51.5	16.2
3.5	7.7	92.3	72.2
5	2.5	97.5	88.1
10	0.05	99.95	99.5
15	0.0	99.99	99.99

An alternative way of describing the statistical properties of the study design is in terms of the true rate based on the observed data. Table 11 shows the exact 2-sided 95% confidence intervals for the probability of an event based on a particular observed rate. For example, if none of the 72 participants using the dapivirine VR experiences a safety event, the 95% exact 2-sided confidence interval for the true rate of event is (0.0%, 4.99%). If we see 2 events, this changes to (0.34%, 9.68%).

Table 11: Exact Two-sided 95% Confidence Intervals Based on Observing a Particular Rate of Safety Endpoints for Arms of Size 72

Observed event rate (%)	Confidence interval (%)
0.0 (0/72)	(0.0, 4.99)
1.4 (1/72)	(0.04, 7.50)
2.8 (2/72)	(0.34, 9.68)

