The primary aim of the study is to compare the safety between the two arms (dapivirine VR arm versus placebo VR arm). Assuming a two-sided Fisher's Exact test with $\alpha = .10$ and 80% or 90% power, Table 12 provides the difference in the rates of safety events (proportion of females experiencing the safety event of interest) between the dapivirine VR arm and the placebo VR arm that is detectable for a given rate in the placebo VR arm. For example, if the true rate of a given toxicity endpoint in the placebo VR arm is 4.2% (1 out of 24 females experiencing a safety event); the proposed sample size provides 90% power to detect safety endpoint rates greater than 30.2% (26.3% with 80% power).

Table 12: Difference in the Rates of Safety Events

Rate in Placebo Arm (%)	Rate in Drug Arm Detectable with 80% Power (%)	Rate in Drug Arm Detectable with 90% Power (%)
4.2 (1/24)	26.3	30.2
8.3 (2/24)	33.0	37.4
20.8 (5/24)	49.5	54.5
41.7 (10/24)	70.6	75.7
62.5 (15/24)	87.8	91.3

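### Fisher's exact test is valid but conservative with 72 vs 24 women; Boschloo's test, built on the two-sided Fisher p-value, is a cheap improvement that never has less power.

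*Protocol*

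**What the plan says.** Protocol section 10.8.2, under Safety Endpoints, tabulates each safety endpoint by arm with exact binomial confidence intervals. It then has Fisher's "exact test used to test for differences in event rates between the two arms". The analysis set is everyone randomized: "All females randomized into the study will be included in the primary analysis according to principle of Intent-to-Treat".

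Section 10.4.1 plans on the same test. The design allocates about 96 women 3:1, which puts 72 on dapivirine and 24 on placebo. The detectable rates are introduced with "Assuming a two-sided Fisher's Exact test with" alpha 0.10, and "Table 12 provides the difference in the rates of safety events" for five placebo rates from 4.2% to 62.5%. For the lowest of these, "the proposed sample size provides 90% power to detect safety endpoint rates greater than 30.2% (26.3% with 80% power").

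The protocol names no unconditional exact test and does not discuss alternatives to Fisher's test.

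**The concern.** Fisher's test conditions on the total number of events. With 24 women in the smaller arm and few events, the attainable p-values are widely spaced, so a nominal 10% test can run well below 10%. In a trial whose primary aim is to compare safety, unused type I error can mean reduced ability to see harm.

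Low rates are plausible here. The primary endpoints are Grade 2 or higher genital, genitourinary and reproductive events judged related to product, and Grade 3 or higher events, in healthy women. Tables 10 and 11 themselves consider event rates from 0.5% and counts of 0, 1 or 2 in 72. The question is how much sensitivity is lost, and whether another exact test recovers it without exceeding 10%.

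**Working it through.** **Inputs.** From sections 10.4.1 and 10.8.2: n1 = 72 (dapivirine), n2 = 24 (placebo), two-sided alpha 0.10, Fisher's exact test, no deduction for dropout.

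**Method.** There are 73 x 25 possible tables (x events of 72, y of 24). For each table the two-sided Fisher p is the sum of the hypergeometric probabilities, given x + y, that are no larger than that of the observed table. For true rates d and a, power = sum over rejected tables of Bin(x; 72, d) x Bin(y; 24, a). Size is the same sum with d = a.

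**Step 1: reproduce Table 12.** With rejection at p <= 0.10, all ten entries give 79.8-80.3% or 90.0-90.2% power, to within about 0.1 point depending on how the placebo rate is rounded. Solving for the first row gives 26.2/30.1, against the stated 26.3/30.2. The table is sound.

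**Step 2: true size of Fisher's test at nominal 10%.**

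| Common rate | 1% | 2% | 4.2% | 8.3% | 10% | 20.8% | 41.7% | maximum |
|---|---|---|---|---|---|---|---|---|
| Size | 1.2% | 2.6% | 4.5% | 5.1% | 5.3% | 7.3% | 8.7% | 8.7% |

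**Step 3: Boschloo's test.** Use the two-sided Fisher p as the statistic, and take the largest cut-off whose rejection probability, maximized over the common rate, stays at or below 0.10. The cut-off is about 0.1255 and the maximum size 9.95%. Because 0.1255 > 0.10 on the same statistic, every table that Fisher rejects is also rejected, so power cannot be lower.

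**Step 4: which tables change.** Against 0/24 the boundary moves from 10/72 to 9/72. Against 1/24 it moves from 15/72 to 14/72. For 9/72 vs 0/24 (9 events in all), the probability that all 9 fall on dapivirine is 0.0656. The opposite-tail terms no larger than this are 0.0337 + 0.0062 + 0.0007 = 0.0406. The Fisher p is therefore 0.0656 + 0.0406 = 0.106. For 14/72 vs 1/24 it is 0.105. Both exceed 0.10 but lie below 0.1255.

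**Step 5: power, Fisher to Boschloo.**

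| Placebo vs dapivirine | Fisher | Boschloo | Gain (points) |
|---|---|---|---|
| 4.2% vs 26.3% (Table 12) | 80.3 | 82.6 | 2.3 |
| 4.2% vs 30.2% (Table 12) | 90.2 | 91.4 | 1.2 |
| 8.3% vs 33.0% (Table 12) | 79.8 | 82.5 | 2.7 |
| 8.3% vs 37.4% (Table 12) | 90.0 | 91.7 | 1.7 |
| 1% vs 12% | 28.9 | 40.3 | 11.4 |
| 1% vs 15% | 53.6 | 64.1 | 10.5 |
| 2% vs 15% | 43.8 | 53.1 | 9.3 |
| 4.2% vs 15% | 27.8 | 34.7 | 6.9 |
| 4.2% vs 20% | 53.4 | 59.1 | 5.7 |
| 8.3% vs 25% | 49.6 | 52.6 | 3.0 |

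In Table 12's last row (placebo 62.5%) the gains are 5.0 and 3.3 points. The first row's detectable rates become about 25.4/29.4.

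Hand check of 1% vs 12%: the newly rejected 9/72 vs 0/24 contributes 0.1396 x 0.7857 = 0.110, and 14/72 vs 1/24 contributes 0.0231 x 0.1905 = 0.004. Together that is 11.4 points, the whole gain.

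**The case against.** The strongest reply is that nothing is wrong. Fisher's test is a valid level-0.10 test, planning and analysis name it consistently, and Table 12 already carries its conservatism. The boundary moves by about one event. Section 10.8.2 also reports counts and exact intervals for each arm, so 9/72 against 0/24 would be visible whatever the p-value, and no go/no-go rule hangs on p < 0.10. All of this stands, and it limits the point to an optional improvement.

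A second reply is that two-sided Boschloo has competing definitions. This also stands. The form built on the doubled one-sided p does not contain Fisher's rejection region: 2/72 vs 3/24 has a two-sided Fisher p of 0.098 (rejected), but its doubled one-sided p is 0.196, above that form's cut-off of 0.1537. The guarantee of no lost power then fails.

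A reader might infer more than the figures support:
- **Double-digit gains wherever placebo events are rare.** These need a placebo rate near 1% and a much higher dapivirine rate. At 1% vs 3% there is no gain, and at Table 12's own low-rate planning points it is 1.2-2.7 points.
- **Boschloo uses up the spare alpha at very low rates.** At a common rate of 1% its size is also 1.2%. The benefit there is power under the alternative only.
- **Table 12 is wrong or the trial is mis-sized.** Table 12 reproduces.

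**Conclusion.** This is a cheap improvement and not an error. At common event rates of 4-10%, Fisher's test runs at about half its nominal 10%. A uniformly no-less-powerful exact test is available within the same 10% limit. The gain is modest at the protocol's low-rate planning points. It is larger, about 7-11 points, when placebo events are rare (1-4.2%) and dapivirine events are at 12-15%. Even there, power reaches only about 35-64%, so the change does not make the trial well powered for such differences.

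The figures assume all 72 and 24 women are analysed, independent binomial outcomes, no adjustment for site, and Boschloo's test defined on the two-sided Fisher p. The placebo rates of 1% and 2% are illustrative assumptions. Table 12 starts at 4.2%.

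**What to change.** Before unblinding, state in section 10.8.2 that the between-arm comparison of each primary safety endpoint uses Boschloo's exact unconditional test, with the two-sided Fisher p-value (not the doubled one-sided p) as its statistic, at two-sided alpha 0.10. Recompute Table 12 in section 10.4.1 under that test, and report Fisher's p-value as supportive.

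The cost is a sentence of analysis text and a recomputed table, with no additional participants or visits. The test is less familiar and needs a maximization over the common event rate, which standard software performs. The software's two-sided definition must be checked against the one named.
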